1. SCHEDULE OF EVENTS

Visit:	Screening & Test Spot	Tx 1¹	Tx 2	FU1
Day:	0	7	21	24
Inclusion/ Exclusion	+			
Informed Consent Form	+			
Demographics, Medical / Medication History, Skin type	+			
Fitzpatrick Wrinkle and Elastosis Scale evaluation	+			+
Test spot	+			
Treatment		+	+	
Subject discomfort assessment (VAS)		+	+	
Subject Self-Report Adverse Event Questionnaire		+ ²	+ ³	+
Subject Tolerability Scale (5-point Likert scale)		+ ²	+ ³	+
Investigator improvement evaluation using GAIS				+
Adverse Events / Concomitant Medications		+	+	+

¹The baseline visit and 1st treatment visit may be scheduled on the same day.

²Telephone call to subject 24 hrs and 72 hrs post first treatment; Subject Tolerability Scale 0; Subject Home Tolerability Scale 24hrs and 72hrs post treatment

³ Telephone call to subject 24 hrs post second treatment; Subject Tolerability Scale 0; Subject Home Tolerability Scale 24hrs post treatment

2. PROTOCOL SYNOPSIS

Study design	Randomized, open-label, multi-centre study to evaluate the tolerability of the application of a combination of a serum containing human bone marrow stem cell derived growth factor and cytokines (SCR Complex™) and a botanical lipid based occlusive (Bio Cel™) following facial fractional RF treatments using the Venus Viva™ SR system. Each subject will receive 2 treatments separated by a 3-week interval. Subjects will complete a VAS and Tolerability Scale immediately following each treatment. Telephone follow-up calls by the site will ask the subject to respond to the Self-Report Adverse Event Questionnaire 24 and 72 hours after the first treatment and 24 hours after the second treatment. Subjects will complete a Home Tolerability Scale 24 and 72 hours after the first treatment and 24 hours after the second treatment. Subjects will return for the final FU visit and be asked to respond to the Self-Report Adverse Event Questionnaire and complete the Home Tolerability Scale for 72 hours. The investigator will also evaluate the subject's improvement using the GAIS at this visit.
Study center / country	2 Study Centres; USA
Study duration	1) For each subject, study duration will be approximately 30 days, including study follow-up. 2) Anticipated start date: July 2016; Anticipated stop date: September 2016.
Investigational product	Venus Viva™ SR system is intended for dermatological procedures requiring ablation and resurfacing of the skin. SCR Complex™ contains human growth factors and cytokines derived through laboratory culture of human bone marrow mesenchymal stem cells. It is indicated for use immediately following and for the first few days of the acute healing phase after treatment with the Venus Viva™ device. Bio Cel™ is a botanical lipid-based gel occlusive. It is indicated for use as an occlusive barrier following ablative and semi-ablative skin treatments, regardless of modality.
Planned number of participants	A total of up to 100 evaluable male or female subjects (Fitzpatrick Skin types I – VI) will be enrolled. Subjects will present with acne scars, general skin texture irregularities and/or rhytides.
Study objectives	Clinical evaluation of the tolerability of using a post-treatment topical adjuvant combination immediately following RF fractional ablation using the Venus Viva™ SR system.
Key Inclusion Criteria	
 • Male or non-pregnant, non-nursing female at least 21 years of age and less than 75 years of age. • Undergoing a dermatological procedure requiring ablation and resurfacing of the facial skin utilizing the Venus Viva™ SR system.
Key Exclusion Criteria	
 • Superficial metal or other implants in the treatment area. • Tattoos, permanent makeup, scars or piercings in the treatment area. • Any active condition in the treatment area, such as sores, psoriasis, eczema and rash.

	
 Any surgical procedure in the treatment area within the last three months or before complete healing.
Primary endpoint	The primary end point will be the tolerability of the application of the stem cell recovery complex (SCR Complex™) and a botanical lipid based occlusive (Bio Cel™) as compared with standard of care immediately following fractional RF treatments.
Secondary endpoints	The secondary outcomes will be the subject's degree of discomfort and/or pain as measured by the visual analogue scale (VAS), the incidence of spontaneous adverse events (AEs) and the investigator's assessment of improvement using the Fitzpatrick Wrinkle and Elastosis Scale scores before and after treatment as well as the Global Aesthetic Improvement Scale (GAIS) for each subject.
Statistical Methodology	
All subjects who received any amount of treatment will be included in the report. The primary outcome measure is the subject's overall tolerability of the adjuvant combination treatment as compared to the standard of care post fractional RF treatment. The self-assessment will be based on a 5-point Likert scale - Subject Tolerability Scale (Appendix A). Summary statistics will be generated for subject tolerability immediately after treatment, 24 hours and 72 hours following treatment as per the terms: Very tolerable, tolerable, having no opinion, intolerable and very intolerable.
 
Summary statistics will also be generated to present the degree of discomfort and/or pain following the procedure, all treatment emergent adverse events (TEAs) and the GAIS scores for the treatment group and standard of care group.

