5. STUDY DESIGN

This is a randomized, open-label, multi-centre study to evaluate the tolerability of the application of a combination of a serum containing human bone marrow stem cell derived growth factor and cytokines (SCR Complex™) and a botanical lipid based occlusive (Bio Cel™) following facial fractional RF

treatments using the Venus Viva™ SR system.

Subjects will be asked to attend up to four visits to the clinic: Screening/consultation, 2 treatment visits - 3 weeks apart and 1 follow-up (FU) visit 3 days after the last treatment. Subjects will also receive a telephone call to evaluate response at 24 hours after each treatment as well as 72 hours after the first treatment. The first treatment visit may occur on the same day as the screening visit. RF treatments will be conducted as detailed in the Venus Viva™ User Manual. For each subject, study duration will be approximately 30 days, including study follow-up. It is anticipated that the study will start July 2016 with an anticipated stop date of September 2016. Changing of these dates will not require a protocol amendment.

Up to 100 healthy subjects from 2 centres who meet the inclusion and exclusion criteria will be enrolled and randomized to the study. The trial will be conducted in compliance with the protocol, GCP and the applicable regulatory requirements. The Sponsor, Venus Concept, will maintain oversight and management of the study.

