11.1 Screening Visit

The following procedures will be performed at the screening visit:

- Written informed consent
- Assign unique identifying number
- Inclusion/exclusion criteria
- Demographics
- Physical examination
- Medical history
- Concomitant medications
- Skin type (Fitzpatrick Scale)
- Wrinkle evaluation (Fitzpatrick Wrinkle and Elastosis Scale)
- Test spot

Test Spot

In order to assess tolerability to treatment, up to three test spots will be performed on the area adjacent to the ear on the side of the neck close to the back (so as it is not visible). Test spots should be based on skin type and desired outcome as per the chart below. The test spots will be used to determine the optimal parameters / setting combinations prior to the first treatment and later, the second treatment.

- Following the test spot, wait to ensure that the chosen parameters indeed lead to the appropriate immediate response.

- If slight erythema and edema and no adverse events occurred, treatment should be continued using the same setting or increase by not higher than ~10% parameters for each session.
- If no results are observed, the treatment parameters should be increased.
- If the patient has experienced adverse events along with improvement, the treatment parameters should be decreased.
- Fine-tuning of the parameters can be done before proceeding to treat the entire sub-area with the chosen parameters. Modification of parameters per treated area within a treatment session should only be carried out if required due to safety concerns.

Assessment of the test spot will be performed following at least 2 hours and up to 48 hours depending on skin type. As such, the first treatment may be conducted on the same day as screening. It is important to not start treatment prior to full evaluation of the reaction to the test spot and having optimal parameters identified.

Table 1 - Test spot and treatment parameter chart

Starting parameters			
Skin Type	Mild	Moderate	Intense
I-II	220v / 30ms	250v / 15ms	280v / 15ms
III-IV	220v / 15ms	240v / 15ms	240v / 30ms
V-VI	220v / 10ms	230v / 5ms	240v / 5ms

Test Spots Mild			
Skin Type	Mild spot 1	Mild spot 2	Mild spot 3
I-II	220v / 5ms	220v / 15ms	220v / 30ms
III-IV	220v / 5ms	220v / 10ms	220v / 15ms
V-VI	220v / 5ms	220v / 8ms	220v / 10ms

Test Spots Moderate			
Skin Type	Moderate spot 1	Moderate spot 2	Moderate spot 3
I-II	250v / 5ms	250v / 10ms	250v / 15ms
III-IV	240v / 5ms	240v / 10ms	240v / 15ms

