11.2 Treatment Visits

Subjects that did not experience significant pain or skin sensitivity in response to the test spots can receive treatments. Each subject will be enrolled and scheduled for two treatments, three weeks apart and return for a follow-up visit three days after the second treatment for evaluation of the treatment area.

The following procedures and assessments are required at the treatment visits:

Pre-treatment

- Confirm continued eligibility regarding inclusion/exclusion criteria
- Review any changes in medication, health status or AE from last visit
- Assessment of adverse events including a photograph of the affected treatment area if an adverse event occurred
- Assessment of concomitant medications
- Assign randomized treatment (after 1st treatment visit only)
- Apply a topical anesthetic preparation over the treatment areas, if required. (If used, record in the CRF.)

Treatment

No lotion, gel or coupling medium is to be used in this treatment. The distal part of the applicator should be clean and dry before fitting it with a new 160 pins tip. The skin in the treated area should also be cleaned well (for removal of any lotions, make-up residues, topical anesthetic cream, etc.) and patted dry. Hairs that exist in the areas should be shaved off.

- Treatment should be performed while the subject is lying down comfortably; the operator should have easy access to the subject's treatment area.
- Areas of dental crowns, caps, braces, or other metal dental implants may be more sensitive to treatment and the clinician may use dental rolls, gauze or a tongue depressor to isolate the area and make the treatment more comfortable (if the face is treated).
- Treatment of subjects in hair-bearing areas may result in some damage to the follicles and subsequent loss of hair. Avoid the beard area (if face is treated) and other hair growing zones if the patient doesn't wish to have reduction of the hair growth. This treatment may also result in in-grown hairs.
- The applicator should be held perpendicular to and in close contact with the skin.
- Pressing the trigger will release the RF energy to the skin, creating a stamped imprint in a shape and intensity depending on energies.

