11.3 Follow-up/Termination Visit

Subjects will be scheduled for a follow-up/termination visit 72 hours after the second treatment. The following procedures will be performed:

- The subject will be asked to report on the comfort(s)/discomfort(s) associated with the second treatment as per the Self-Report Adverse Event Questionnaire.
- Wrinkle evaluation (Fitzpatrick Wrinkle and Elastosis Scale)
- Global Aesthetic Improvement (GAI) Scale (Appendix D) as evaluated by the investigator.
- Subject Tolerability Scale 72 hours post second treatment
- Assessment of concomitant medications

The subject's participation in the study is now complete. In case of early termination, the date and reason for early termination will be recorded in the CRF. Subjects will also be asked to return to the clinic to complete follow-up/termination visit procedures.

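### The Schedule of Events puts the two treatments 14 days apart, while the text says three weeks, so subjects not treated on Day 0 could be re-treated early

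*Combined protocol and SAP*

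**What the plan says.** Three places give the interval between treatments in words, and they agree:

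- Section 2 (Protocol Synopsis, Study design): "Each subject will receive 2 treatments separated by a 3-week interval".
- Section 5 (Study Design): "2 treatment visits - 3 weeks apart and 1 follow-up (FU) visit 3 days after the last treatment".
- Section 11.2 (Treatment Visits): each subject is to be "scheduled for two treatments, three weeks apart".

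The Schedule of Events in Section 1 gives day numbers instead: screening and test spot on Day 0, Tx 1 on Day 7, Tx 2 on Day 21 and FU1 on Day 24. Footnote 1 permits the baseline visit and Tx 1 to share a day. No visit windows are given, and nothing says whether Days 21 and 24 count from screening or from Tx 1.

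Section 11.1 governs how soon Tx 1 can follow screening: "Assessment of the test spot will be performed following at least 2 hours and up to 48 hours depending on skin type". It concludes that a same-day first treatment is possible, and then warns: "It is important to not start treatment prior to full evaluation of the reaction to the test spot".

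Section 11.3 fixes the last visit relative to Tx 2: "Subjects will be scheduled for a follow-up/termination visit 72 hours after the second treatment".

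**The concern.** The printed days for Tx 1 and Tx 2 contradict the stated interval. The Schedule of Events is the only place with numbered visit days, so a site could reasonably book from it. A subject whose Tx 1 falls after Day 0 and whose Tx 2 is held at Day 21 would then have facial ablation repeated sooner than the text intends.

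The conflict also leaves compliance undefined. With Tx 1 on Day 7, a second treatment on Day 21 departs from the text, and one on Day 28 departs from the table. Section 15 asks sites to explain visits made outside the protocol's time frame, and Section 17 bars deviations without prior sponsor approval except to remove an immediate hazard. Neither a site nor a monitor can tell which date is the deviation, and the two centres could settle it differently.

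Three things are at stake: consistency of the regimen, recovery time before the second ablation, and the timing relative to Tx 1 of the two secondary outcomes scored at FU1 (Fitzpatrick wrinkle score and GAIS).

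**Working it through.** **Inputs**

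- Table days (Section 1): screening 0, Tx 1 = 7, Tx 2 = 21, FU1 = 24.
- Stated interval (Sections 2, 5 and 11.2): three weeks = 21 days.
- Stated gap from Tx 2 to FU1 (Sections 5 and 11.3): 3 days.
- Earliest Tx 1: Day 0 (footnote 1 and Section 11.1).
- Test-spot reading: 2 to 48 hours, that is, up to Day 2 (Section 11.1).

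**Step 1. Can the stated interval be reproduced from the table?**

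- As printed: Tx 2 - Tx 1 = 21 - 7 = 14 days, against 21. The shortfall is 7 days, and 7/21 = 33%.
- With Tx 1 moved to Day 0 under footnote 1: 21 - 0 = 21 days, which agrees.
- FU1 - Tx 2 = 24 - 21 = 3 days, which agrees.

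So the FU1 cell is right relative to Tx 2, and it must move whenever Tx 2 moves.

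**Step 2. General case.** Let Tx 1 fall on Day d, with Tx 2 and FU1 held at Days 21 and 24. Then:

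- interval by table = 21 - d
- FU1 after Tx 1, by table = 24 - d
- FU1 after Tx 1, by text = 21 + 3 = 24 for every d
- days that satisfy the text: Tx 2 = d + 21, FU1 = d + 24

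| Tx 1 day (d) | Tx 1 to Tx 2 by table | Short of 21 by | FU1 after Tx 1 by table | Tx 2 / FU1 day by text |
|---|---|---|---|---|
| 0 | 21 | 0 | 24 | 21 / 24 |
| 1 | 20 | 1 | 23 | 22 / 25 |
| 2 (48-hour limit) | 19 | 2 | 22 | 23 / 26 |
| 7 (as printed) | 14 | 7 | 17 | 28 / 31 |

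The shortfall equals the day number of Tx 1. The table meets the text only at d = 0.

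**Step 3. Does the stated duration settle it?** The synopsis says: "For each subject, study duration will be approximately 30 days, including study follow-up". Under a three-week interval the last visit is on Day 24 if Tx 1 is on Day 0, or Day 31 if Tx 1 is on Day 7. Day 31 is close to 30, but a Day 0 start is also permitted and gives 24. The conclusion does not rest on this figure.

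**The case against.** The arithmetic is not in dispute. The case for treating this as trivial has five parts.

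1. *The table is only a summary.* Section 11 describes Section 1 as summarising which procedures are done and how often, whereas Section 11.2 gives the scheduling instruction, and it says three weeks. A site would have to follow one row against three consistent statements. This stands in part: early re-treatment is possible, not certain. But the table is the only source of day numbers, and it has no windows.
2. *Same-day treatment is expressly allowed.* Section 11.1, Section 5 and footnote 1 all permit it, and Days 21 and 24 are then correct. A subject who needs the full 48 hours loses only 2 days. This is true, and the 14-day figure applies only to a Day 7 start. But Day 7 is the day the table prints for Tx 1, and a wait that varies by skin type means a Day 0 start cannot be assumed for everyone when skin types I to VI are enrolled. The documents do not say how many subjects would start on each day.
3. *Safety checks precede each treatment.* Section 11.2 requires eligibility, health status and adverse events to be reviewed, and an active skin condition in the treatment area is an exclusion. This does reduce the risk of treating visibly unhealed skin. It does not restore the intended interval.
4. *Nothing in the analysis depends on it.* Both arms share the schedule, tolerability and VAS are timed from each treatment, and no method in Section 14 uses study day. This stands in full.
5. *The 30-day duration points to Day 31.* It does fit 7 + 21 + 3 = 31, and so supports three weeks as the intended interval. That supports the correction and leaves the printed row wrong.

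**Conclusion.** The concern holds and should be fixed. The Day row gives 14 days between treatments where the text gives 21. Booked by table days, the interval is 21 days for a Day 0 start, 20 for Day 1, 19 for Day 2 and 14 for Day 7. FU1 falls 24, 23, 22 or 17 days after Tx 1 respectively, instead of 24 throughout.

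This rests on two assumptions: that a site holds Tx 2 and FU1 at the printed days counted from screening, and that three weeks is the intended interval. The second has the support of every statement in words; no section says two weeks.

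The consequence is limited. The row does not by itself bias the between-arm comparison, and no sample size or power figure changes. Nor do the documents show that 14 and 21 days differ clinically: the common local effects described in Section 12 and Appendix B last up to about a week.

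**What to change.** In the Day row of Section 1, replace the fixed Days 21 and 24 with:

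- Tx 2 = Tx 1 + 21 days
- FU1 = Tx 2 + 3 days

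This gives Days 21 and 24 when Tx 1 is on Day 0, and Days 28 and 31 when it is on Day 7, so the same-day option in footnote 1 is kept. The sponsor should confirm that three weeks is intended. Stating visit windows at the same time would be useful, since none are given.

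The core cost is two cells in one table row. Analysis, sample size and procedures are unchanged.

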3. INTRODUCTION

Radiofrequency (RF) devices are safe and effective. The RF energy is delivered to the skin in a chromophore non-specific manner, heating the underlying dermal tissue at different levels. This heat results in a wide range of mechanisms from stimulation to ablation. The RF Scan delivers RF energy in a non-homogenous fractional form, selectively heating the dermis while protecting the overlying epidermis. The array of multi-electrode pins delivers bipolar RF energy to dry, non-moisturized skin. The procedure is carried out while leaving areas that have been exposed to slight impact, in-between the targeted areas, which help to maintain the integrity of the treated skin and serve as a reservoir of cells that accelerate and promote the healing process.

SCR Complex™: The cells of our bodies communicate with one another using a complex bio-molecular language. Growth factors and cytokines are the "words" that control embryogenesis, growth, immunologic defenses, and tissue healing. Of the more than 200 types of cells in the body, bone marrow mesenchymal stem cells are the ones that act as commander-in-chief of healing in all tissues, including skin. These cells are mobile, migrating from the bone marrow into the blood stream where they gain access to all parts of the body. When they encounter injury, they serve as smart local "drugstores", secreting pro-healing anti-inflammatory bio-signals. The number of these cells plummets with age, accounting in large measure for the less robust healing of later decades. Topical application of growth factors and cytokines obtained through laboratory culture of bone marrow stem cells is thought to improve the appearance of the signs of aging skin.

Because aging skin is injured skin, some benefit has been seen with the topical application of bone marrow stem cells bio-signal products in anti-aging formulations. Improvement has also been seen when used with dermal needling, and with fractional CO2 laser resurfacing in which "downtime" has been reduced by up to 40%.

Bio Cel™: Ablative and semi-ablative skin treatments result in increased trans-dermal water loss and potential for environment contamination. Occlusive dressings are typically used as part of post-procedure treatment of treated skin. Bio Cel™ occlusive gel is based on botanical lipids instead of petroleum, and has been used with benefit for over two years following laser resurfacing treatments. A boron-based molecule (hydrogen orthoborate) adds analgesic, anti-inflammatory, and bacteriostatic benefit. Tocopherol acetate (vitamin E) helps reduce erythema, edema, and acts as an antioxidant against free radical damage. Recombinant TGB-beta 3 provides anti-inflammatory benefit.

4. PURPOSE

The purpose of the study is to compare the tolerability of the application of a combination of a serum containing human bone marrow stem cell derived growth factor and cytokines (SCR COMPLEX™) and a botanical lipid-based occlusive (Bio Cel™) immediately following fractional RF treatment using the Venus Viva™ versus standard of care.

5. STUDY DESIGN

This is a randomized, open-label, multi-centre study to evaluate the tolerability of the application of a combination of a serum containing human bone marrow stem cell derived growth factor and cytokines (SCR Complex™) and a botanical lipid based occlusive (Bio Cel™) following facial fractional RF

treatments using the Venus Viva™ SR system.

Subjects will be asked to attend up to four visits to the clinic: Screening/consultation, 2 treatment visits - 3 weeks apart and 1 follow-up (FU) visit 3 days after the last treatment. Subjects will also receive a telephone call to evaluate response at 24 hours after each treatment as well as 72 hours after the first treatment. The first treatment visit may occur on the same day as the screening visit. RF treatments will be conducted as detailed in the Venus Viva™ User Manual. For each subject, study duration will be approximately 30 days, including study follow-up. It is anticipated that the study will start July 2016 with an anticipated stop date of September 2016. Changing of these dates will not require a protocol amendment.

Up to 100 healthy subjects from 2 centres who meet the inclusion and exclusion criteria will be enrolled and randomized to the study. The trial will be conducted in compliance with the protocol, GCP and the applicable regulatory requirements. The Sponsor, Venus Concept, will maintain oversight and management of the study.

